## 2.3 Exploratory Objectives

The exploratory objectives are to evaluate:

- Difference in health-related quality of life using the subject-completed chronic liver disease questionnaire (CLDQ) following administration of GR-MD-02 or placebo at 1 year
- Baseline-adjusted change in FibroTest (FibroSure) and the enhanced liver fibrosis (ELF) score at Infusion Visits 7, 13, 20, and 14-28 days after final infusion
- Changes in liver biopsy staining for alpha smooth muscle actin and galectin-3 in subjects treated with GR-MD-02 or placebo at 1 year

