#### **6.1.3.3 Infusion Visit 1 (Week 1)**

During the Infusion 1 Visit, the following procedures and assessments will be performed after randomization and prior to administration of IMP ([Table 12-2](#)):

- Enter the IWRS and register subject visit data.
- CLDQ (This questionnaire will be given to the subject at the beginning of the visit and will be considered source documentation.)
- Alcohol timeline followback (TLFB) (This will be given to the subject at the beginning of the visit and will be considered source documentation.)

- Perform a limited physical examination (including weight and examination of the heart, lung, and abdomen).
- Collect vital sign measurements (including heart and respiratory rate, blood pressure, and body temperature).
- Perform hematology testing.
- Perform blood chemistry testing.
- Collect biomarkers blood sample (will include the ELF test and FibroTest [FibroSure], and galectin-3).
- Collect plasma and serum sample for storage at  $-20^{\circ}\text{C}$ .

The following information will be collected after IMP administration:

- AE monitoring.
- Record concomitant medications.

The following will be performed 2 hours after the end of the IMP infusion:

- Collect PK sample.

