### **6.1.3.7 Infusion Visit 13 (Week 25 ± 3 Days)**

The following procedures and assessments will be performed prior to administration of IMP:

- Enter the IWRS and register subject visit data.
- Alcohol TLFB (This questionnaire will be given to the subject at the beginning of the visit and will be considered source documentation.)
- Assessment of cirrhosis complications.
- Perform a limited physical examination (including weight and examination of the heart, lung, and abdomen).
- Collect vital sign measurements (including heart and respiratory rate, blood pressure, and body temperature).
- Perform urine pregnancy test (females of childbearing potential only).
- Perform hematology testing.
- Perform blood chemistry testing.
- Obtain MELD score.
- Conduct a FibroScan.
- Perform MBT (if available).
- Collect biomarkers blood sample (will include the ELF test, FibroTest [FibroSure], and galectin-3).
- Collect plasma and serum sample for storage at  $-20^{\circ}\text{C}$ .

The following information will be collected after IMP administration:

- Perform a 12-lead ECG assessment.
- Obtain Child-Turcotte-Pugh score and class (A, B, or C).
- AE monitoring.
- Record concomitant medications.

The following will be collected 2 hours after the end of the IMP infusion

- Collect PK sample

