### **7.3 Exploratory Endpoints**

Exploratory endpoints are to evaluate:

- Difference in health-related quality of life (using the subject-completed CLDQ) following administration of GR-MD-02 or placebo at 1 year
- Baseline-adjusted change in FibroTest (FibroSure) and ELF score at Infusion Visits 7, 13, 20, and 14-28 days after final infusion
- Changes in liver biopsy staining for alpha smooth muscle and galectin-3 in subjects treated with GR-MD-02 or placebo at 1 year
  - HVPG  $\geq 10$  and  $< 15$  mm Hg (elevated portal pressure, with potential development of varices, classified as clinically significant portal hypertension)
  - HVPG  $\geq 15$  (increased incidence of complications from varices)

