e Vital sign measurements include heart and respiratory rate, blood pressure and body temperature prior to IMP administration. Blood pressure will be obtained with the subject in the supine position and measured twice consecutively with a 1-minute interval between measurements. The average of the 2 measurements will be recorded.

- f Hematology will include complete blood cell count with differential (red blood cells, white blood cells, , red cell indices, platelets, hemoglobin, and hematocrit).
- g Blood chemistry will include alanine aminotransferase, aspartate aminotransferase, albumin, alkaline phosphatase, bicarbonate, blood urea nitrogen, calcium, chloride, creatinine, glucose, lactate dehydrogenase, magnesium, phosphorus, potassium, sodium, total and direct bilirubin, total protein, uric acid,  $\gamma$ -glutamyl transferase, and fasting insulin level. Subjects must be in a fasted state prior to blood collection.
- h Biomarker blood tests will include the enhanced liver fibrosis test, FibroTest (FibroSure), and galectin-3 and will occur prior to first infusion and at Infusion Visits 13 and 14 to 28 days following final 26th infusion.
- i IMP administration will occur after the following procedures: limited physical examination, vital sign measurements, hematology, blood chemistry, and biomarker blood samples.
- j Within 14 to 28 days after the final 26th dose of IMP or where feasible following study termination due to the occurrence of a clinical event or withdrawal of consent. EGD must be performed on a different day within the 14- to 28-day follow-up period than when the HVPG assessment is performed.
- k The PK sample will be collected 2 hours after the end of the IMP infusion.

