3.2.3. Exploratory Endpoints

- Difference in health-related quality of life (using the subject-completed CLDQ) following administration of GR-MD-02 or placebo at 1 year
- Baseline-adjusted change in FibroTest (FibroSure) and ELF score at Infusion Visits 7, 13, 20, and 14 to 28 days after final infusion
- Changes in liver biopsy staining for α -SMA and galectin-3 in subjects treated with GR-MD-02 or placebo at 1 year

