8.3. Exploratory Endpoints

Each of the following exploratory efficacy endpoints will be analyzed analogous to the primary efficacy endpoint, using the ANCOVA model unless otherwise specified. For each endpoint, the baseline value of the endpoint will be used as a continuous covariate in the ANCOVA model.

- Difference in health-related quality of life (using the subject-completed CLDQ) following administration of GR-MD-02 or placebo at 1 year
- Baseline-adjusted change in FibroTest (FibroSure) and ELF score at Infusion Visits 7, 13, 20, and 14-28 days after final infusion
- Changes in liver biopsy staining for α -SMA and galectin-3 in subjects treated with GR-MD-02 or placebo at 1 year will be evaluated using robust regression (M estimation method)

CLDQ

CLDQ is a self-administered questionnaire that consists 29 items on a seven-point scale, ranging from the worst (1) to the best (7) possible function. The questionnaire includes following 6 domains:

Domains	Items
Abdominal symptoms (AS)	1, 5, 17
Fatigue (FA)	2, 4, 8, 11, 13
Systemic symptoms (SS)	3, 6, 21, 23, 27
Activity (AC)	7, 9, 14
Emotional function (EF)	10, 12, 15, 16, 19, 20, 24, 26
Worry (WO)	18, 22, 25, 28, 29

Average score of each domain will be computed. The average score across six domain average scores will also be derived as the overall average score. The derived domain average and overall average score will be summarized at scheduled visits. If the score is missing for some individual items, the domain average score should be calculated as an average of available items if more than 50% of items in that domain are available. If 50% or less of the items are available for a domain, the domain average score is set as missing too.

FibroTest (FibroSure) and ELF Score

Missing values will be imputed using the LOCF method for the post-baseline visits for FibroTest score and ELF score. Also, the ANCOVA model will be conducted for both observed values and LOCF values.

Treatment effects for FibroTest score and ELF score overtime will be estimated using MMRM analysis with the FAS population respectively.

Each exploratory test will also be summarized for the FAS population at all scheduled visits, along with the change from baseline descriptively in summary tables.

9. Safety Analysis

All analysis of safety will be conducted using the Safety set.

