9.3. Biomarker Measurements

A blood sample will be collected for assessment of galectin-3 at Infusion Visits 1, 7, 13, 20, and 14 to 28 days after final infusion. Summary statistics of the observed values and change from baseline will be provided at the scheduled visits for the safety population.

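### FibroTest and ELF change is an endpoint at Infusion Visits 7 and 20, but the protocol schedules no biomarker sample at either visit

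*Protocol*

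**What the plan says.** **Endpoint visits.** The protocol synopsis (exploratory objectives) and section 2.3 set the assessment times for both scores: "Baseline-adjusted change in FibroTest (FibroSure) and the enhanced liver fibrosis (ELF) score at Infusion Visits 7, 13, 20, and 14-28 days after final infusion". Section 7.3 repeats them as an endpoint, and SAP 2.3, 3.2.3 and 8.3 use the same visit list.

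**Sampling visits.** Footnote h of protocol Table 12-2 states that the biomarker tests "will occur prior to first infusion and at Infusion Visits 13 and 14 to 28 days following final 26th infusion". The biomarker row of the table agrees with it, as does the study design part of the synopsis. Among the visit descriptions, section 6.1.3.3 (Visit 1), section 6.1.3.7 (Visit 13) and section 6.1.4 (follow-up) order the sample; the Visit 13 entry reads "Collect biomarkers blood sample (will include the ELF test, FibroTest [FibroSure], and galectin-3". Sections 6.1.3.5 (Visit 7) and 6.1.3.9 (Visit 20) order hematology and chemistry but no biomarker sample.

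**Analysis.** SAP 8.3 says "Missing values will be imputed using the LOCF method for the post-baseline visits for FibroTest score and ELF score". It then plans ANCOVA on both observed and LOCF values, and an MMRM in the full-analysis set.

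**A different schedule in the SAP.** SAP 9.3 has blood taken for galectin-3 "at Infusion Visits 1, 7, 13, 20, and 14 to 28 days after final infusion". It does not name FibroTest or ELF.

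**The concern.** The endpoint and the schedule cannot both be followed. Protocol section 6.3.2 refers the reader to Table 12-2 for biomarker timing, so a site would take its instructions from the table and would not draw the sample at Visits 7 and 20. The visit list is stated the same way in both documents, so it is unlikely to be a slip in one place.

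At stake is the time course of two noninvasive fibrosis scores. FibroTest is the marker for which the protocol's introduction reports a dose-dependent Phase 1 reduction, so its early and intermediate values have some interest. A second risk lies in the analysis: an imputation rule applied to a visit that nobody sampled could produce a tabulated result containing no measurement from that visit.

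**Working it through.** No sample size, power or alpha figure is involved. The check sets the endpoint visits against the sampling visits, asks whether other samples could fill a gap, and follows the analysis rules through.

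**1. Visits side by side** (weeks from Table 12-2)

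| Time point | Week | FibroTest/ELF endpoint | Biomarker sample in protocol | Galectin-3 draw in SAP 9.3 |
|---|---|---|---|---|
| Visit 1 | 1 | baseline | yes | yes |
| Visit 7 | 13 | yes | **no** | yes |
| Visit 13 | 25 | yes | yes | yes |
| Visit 20 | 39 | yes | **no** | yes |
| Follow-up | 53-55 | yes | yes | yes |

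On the protocol schedule, 2 of the 4 post-baseline endpoint times lack a sample. If FibroTest and ELF were drawn whenever SAP 9.3 draws galectin-3, the count would be 0 of 4.

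**2. Could other blood work supply the scores?**
- FibroTest needs five laboratory inputs (protocol 6.3.2.2). Haptoglobin, gamma-glutamyl transferase and total bilirubin are in the safety panels (6.4.8, 6.4.9). Alpha-2-macroglobulin and apolipoprotein A1 are not.
- ELF needs three markers (6.3.2.1), none of which is in the safety panels.
- Stored plasma and serum are taken at Visits 1, 13 and 26 (6.3.3), so they cannot be assayed later for Visits 7 or 20.

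**3. What the planned analyses would do on the protocol schedule**, assuming no unscheduled or early-termination sample happens to fall in between:
- Observed-value ANCOVA: no data at Visits 7 and 20, so it cannot be run there.
- MMRM: it can be fitted to Visit 13 and follow-up, but has no data from which to estimate an effect at Visits 7 or 20.
- LOCF at Visit 20: the last value is from Visit 13, carried 39 - 25 = 14 weeks. The carried change equals the Visit 13 change for every subject, so the Visit 20 LOCF ANCOVA would repeat the Visit 13 LOCF ANCOVA.
- LOCF at Visit 7: there is no earlier post-baseline value. If baseline may not be carried, Visit 7 stays missing. If it may, the Visit 1 value is carried 13 - 1 = 12 weeks and the change is exactly 0 for every subject, which leaves no variation to test. SAP 8.3 does not say which applies.

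**4. On the SAP 9.3 schedule**, if it extends to FibroTest and ELF, all four times could be measured and LOCF would fill only sporadic gaps.

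**The case against.** The strongest reply is that the SAP and this protocol are not a matched pair. The supplied protocol is marked Original and dated 20 February 2015. The SAP departs from it elsewhere: it admits Ishak stages 5 and 6 only, adds two histological staging endpoints, and has a different pharmacokinetic sampling plan with nondosing visits. The protocol takes galectin-3, FibroTest and ELF as one biomarker sample, so the galectin-3 draws that SAP 9.3 places at Visits 7 and 20 suggest that the SAP authors expected all three tests there.

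This has force. A reader might infer that LOCF will fabricate the Visit 7 and Visit 20 results. The documents do not support that, for four reasons:
- It joins the SAP's imputation rule to a sampling schedule that the SAP itself does not repeat.
- Visit 7 has no earlier post-baseline value to carry.
- A sample that was never scheduled is not clearly a missing value in the SAP's sense.
- The observed-value ANCOVA and the MMRM are planned alongside LOCF, and the empty observed analysis would expose the gap.

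It is also true that these endpoints are exploratory and lie outside the gatekeeping sequence.

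The reply does not remove the contradiction inside the protocol, whose own endpoint list and sampling schedule disagree. That a later protocol version added the draws is an inference; none was supplied. SAP 9.3 names only galectin-3, so even the SAP does not expressly schedule FibroTest or ELF at Visits 7 and 20.

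**Conclusion.** The point holds as an internal contradiction. FibroTest and ELF change is promised at four post-baseline times, and the protocol schedules the sample at two of them. The missing values could not be recovered from the safety laboratory panels or from stored samples.

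The analysis consequences are conditional. They require that the protocol schedule was the one followed and, for the Visit 20 copy of Visit 13, that LOCF is applied to an unscheduled visit. If the three biomarker tests were in fact drawn on the SAP 9.3 schedule, those consequences disappear and only the texts need aligning.

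The weight is modest: two exploratory endpoints, with no effect on the primary analysis, the gated secondary analyses, the type I error or the sample size. It should still be corrected, because the protocol as written cannot deliver its own endpoint and the correction is cheap.

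**What to change.** Reconcile the passages in one of two ways.

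1. **Add the sample at Visits 7 and 20.** Change the biomarker row and footnote h of Table 12-2, sections 6.1.3.5 and 6.1.3.9, and the study design part of the synopsis. Have SAP 9.3 state that FibroTest and ELF are drawn together with galectin-3. Both visits already draw blood, so the cost is the assays: three tests at two visits, or at most 156 x 2 x 3 = 936 test results before dropout. If a later protocol version already contains these draws, the SAP should identify it as the governing version.
2. **Remove Visits 7 and 20.** Delete them from the synopsis objectives and from protocol 2.3 and 7.3; from SAP 2.3, 3.2.3 and 8.3, including the ANCOVA, LOCF and MMRM for those visits; and from the galectin-3 list in SAP 9.3. The cost is wording only, with the loss of one early and one intermediate time point.

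In either case, SAP 8.3 should state that LOCF applies only at visits with a scheduled sample, say whether a baseline value may be carried forward, and rule out reporting a carried value as the result of a visit where no sample was scheduled.

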## 2.4 Safety Objectives

The safety objectives are to assess the safety and tolerability of GR-MD-02 versus placebo at 1 year.

## 2.5 Pharmacokinetic Objective

The pharmacokinetic (PK) objectives are to evaluate systemic exposure following multiple doses of GR-MD-02 in subjects with portal hypertension due to NASH cirrhosis and to explore the population pharmacokinetics of GR-MD-02 in subjects with NASH with portal hypertension and cirrhosis or advanced bridging fibrosis.

Note: Formal population PK analysis will not be performed in this study. However, GR-MD-02 plasma levels will be used to evaluate systemic exposure following multiple doses. In the Phase 1 clinical study ([Galectin 2014](#)), the observed maximum plasma or serum concentration after administration ( $C_{max}$ ) drug levels for all doses were well correlated with the area under the concentration-time curve ( $h \cdot \mu\text{g/mL}$ ) ( $p < 0.001$ ,  $r^2 = 0.91$ ). Therefore,  $C_{max}$  plasma levels at 2 hours following the dose of GR-MD-02 will be used to estimate the systemic exposure of the drug. Plasma levels of GR-MD-02 will be evaluated at the initiation of the study in all subjects, 2 hours after investigational medicinal product (IMP) infusion at Infusion Visits 1, 2, 3, 4, 7, 10, 13, and 26. Trough levels of drug will not be informative, since there were only measurable levels of drug detected through 72 hours following a dose and were thereafter undetectable (assay limit of detection of 1.2  $\mu\text{g/mL}$ ).

[figure not shown]
### **3 Investigational Plan**

#### **3.1 Study Design**

Study GT-026 is a Phase 2, multicenter, parallel-group, North American, randomized, placebo-controlled, double-blind study of subjects with portal hypertension due to advanced bridging fibrosis or cirrhosis. The study will be conducted in 45 to 60 study centers in the United States and Canada.

This study will enroll subjects with portal hypertension (HVPG greater than or equal to 6 mm Hg) who also have a liver biopsy showing cirrhosis (Ishak stage 5 or 6), or advanced bridging fibrosis (Ishak stage 4) presumably due to NASH, excluding subjects with medium and large varices and those with decompensated cirrhosis (as defined by the presence of clinically detectable ascites, any episode of variceal bleeding, and overt hepatic encephalopathy). Subjects with portal hypertension and the appropriate biopsy findings will be randomly assigned (1:1:1) to receive 1 of 3 treatment assignments: placebo, GR-MD-02 in a dose of 2 mg/kg lean body mass, or GR-MD-02 in a dose of 8 mg/kg lean body mass administered every other week over a 52-week period for a total of 26 infusions ([Figure 3-1](#)). The primary endpoint analysis is the baseline-adjusted change in HVPG at 1 year (53 - 55 weeks) in subjects treated with placebo as compared to subjects treated with GR-MD-02 (2 mg/kg/week or 8 mg/kg/week). The model will include treatment group at randomization and the baseline HVPG as a covariate.

**Figure 3-1 Study Design GT-026**

[figure not shown]

Abbreviations: EGD, esophagogastroduodenoscopy; HVPG, hepatic venous pressure gradient; LB, liver biopsy (percutaneous or transjugular)

The study will include prescreening, screening, randomization, treatment, and follow-up periods. No dose modification for GR-MD-02 will be allowed.

A flow chart depicting the prescreening and screening procedures is provided in [Figure 3-2](#).

**Figure 3-2 Prescreening and Screening Flow Chart GT-026**

Abbreviations: EGD, esophagogastroduodenoscopy; HVPG, hepatic venous pressure gradient; NASH, nonalcoholic steatohepatitis

Note: C-methacetin breath test (if available) to be performed before either EGD, liver biopsy, or HVPG at investigator's discretion.

**Prescreening:** Prescreening may begin at Week -9. Prior to beginning prescreening procedures, the subject must sign the informed consent form (ICF). Criteria have been established to avoid unnecessary medical procedures (HVPG, esophagogastroduodenoscopy [EGD] and biopsy) in subjects who have a high likelihood of not meeting key study requirements. Subjects who have had a previous liver biopsy with a diagnosis of NASH with either advanced bridging fibrosis (Ishak stage 4) or cirrhosis (Ishak stage 5 or 6) are eligible to move forward to screening. Subjects with a presumptive clinical diagnosis of NASH (based on the assessment of the principal investigator) will have a FibroScan to assess the potential for fibrosis. Subjects who have a FibroScan score of at least 12.0 kiloPascals (kPa) will be considered to have advanced fibrosis and will proceed to screening. Likewise, subjects with a documented qualifying FibroScan score within the previous 12 months of screening may proceed to screening.

**Screening:** The screening window is up to 8 weeks.

Subjects will undergo the following required procedures to assess eligibility during the screening period: HVPG measurement, liver biopsy, and EGD. Additionally, at the time of 1 of these 3 procedures (at the discretion of the investigator), subjects will have a MBT performed (if available) prior to the procedure. Eligible subjects will have both an HVPG screening measurement of at least 6 mm Hg and a liver biopsy with advanced bridging fibrosis (Ishak stage 4) or cirrhosis (Ishak stage 5 or 6), presumably due to NASH. Central reading groups will be used to assess the appropriateness of biopsy and HVPG measurements. A liver biopsy diagnosis of advanced bridging fibrosis or cirrhosis, presumably due to NASH, will include the following 2 categories:

1. Cirrhosis or advanced bridging fibrosis with a definitive pathological diagnosis of NASH (presence of fat, ballooning degeneration, and inflammation) or;
2. Cirrhosis or advanced bridging fibrosis wherein the subject has greater than 5 years of obesity (body mass index [BMI] >30) and/or diabetes with negative viral hepatitis markers and a biopsy showing cirrhosis or advanced bridging fibrosis with any amount of fat

Subjects who meet all of the inclusion criteria and none of the exclusion criteria will proceed to randomization and the treatment phase. Subjects who fail to meet eligibility criteria due to an abnormal laboratory result may undergo retesting of the abnormal laboratory parameter during the screening window and at the discretion of the investigator and with prior approval of the medical monitor.

**Treatment Phase:** Subjects with portal hypertension who meet all of the other criteria for study inclusion will be randomly assigned (1:1:1) to receive 1 of 3 treatment assignments including placebo, GR-MD-02 in a dose of 2 mg/kg lean body mass, or GR-MD-02 in a dose of 8 mg/kg lean body mass administered every other week over a 52-week period for a total of 26 infusions. During the treatment phase of the study, all subjects randomly assigned to IMP will attend study visits according to the schedule of visits for study administration and monitoring (Table 12-2). Safety (12-lead electrocardiogram [ECG], physical examinations, vital sign measurements, adverse event [AE] monitoring, and safety laboratory assessments), and efficacy (FibroScan, MBT (if available), biomarkers, assessment of cirrhosis complications [esophageal variceal hemorrhage or portal hypertensive gastropathy

hemorrhage, clinically apparent ascites, spontaneous bacterial peritonitis, overt hepatic encephalopathy, listing for a liver transplant or the performance of a liver transplant], and quality of life) will be monitored throughout the treatment phase.

**Postdose Final Visit (14-28 days):** All subjects will attend a visit (or visits) 14 to 28 days after final dose. During this visit, safety (AE monitoring and safety laboratory assessments) and efficacy (FibroScan, MBT [if available], biomarkers, EGD, HVPG, and a liver biopsy) assessments will be collected/performed ([Table 12-2](#)).

**Follow-up/Early Termination Visit:** All subjects are to attend a follow-up/early termination visit 14 days after the postdose final visit to evaluate safety. During this visit, a 12-lead ECG, a physical examination, vital sign measurements, and AE monitoring will be collected/performed ([Table 12-2](#)).

**Open-Label Extension Study:** Following study completion, subjects will be offered enrollment into a subsequent separate study, an open-label extension study (OLES), if there is adequate tolerability and no safety issues or signs of clinical progression that would require discontinuation.

**End-of-Study Telephone Contact:** Subjects who do not enroll into the OLES will be contacted via telephone every 6 months for 2 years, and annually thereafter for a total of 4 years, for a brief update and are to be assessed for survival, listing for a liver transplant or the performance of a liver transplant, or complications of chronic liver disease (ascites, spontaneous bacterial peritonitis, variceal bleeding, and encephalopathy; [Table 12-3](#)).

